Research setting. The study will be conducted in Wakiso District, Uganda which is on the northern side of Lake Victoria. Our team has conducted several studies in fishing communities in this district. Majority of residents of fishing villages work in the fishing industry and individuals receive daily cash payments for their work. The study will take place at 5 HIV clinics in Wakiso District which serve large populations of fisherfolk. *Fisherfolk* include fishermen, fish traders, fish processors, fish loaders, boat/fishing equipment repairmen, and other workers who engage in work supporting the fishing industry within the fishing communities. As of May 2018, there were over 1,700 adult male patients on ART at these clinics.

Study population. The study population is fisherfolk men aged 18-50 who engage in heavy alcohol use. The age range focuses on men who are the most high risk group for HIV and unhealthy alcohol use.^{5, 9}

Inclusion criteria: men aged 18-50; work as a fisherman, fish trader, fish processor, fish loader, related occupation supporting the fishing industry; living with HIV; on antiretroviral treatment for at least 1 month, report missing 1 or more dose of ART in the prior 2 weeks; **Alcohol use criteria:** consumed 5 or more drinks per occasion 2 or more times in the prior month or have an AUDIT-C (Alcohol Use Disorder Identification Test-Concise) score of ≥ 4 ¹⁹; not planning to move from the area within the next 6 weeks; have their own mobile phone and can be reached via phone (nearly all ($>97\%$) fisherfolk men have their own mobile phones and receive incoming calls is free).

Consuming ≥ 5 drinks per occasion is the definition of heavy episodic drinking or binge drinking, as defined the National Institutes of Alcohol Abuse and Alcoholism (NIAAA). This type of drinking is the most concerning type of alcohol use for individuals who are HIV positive. Recent longitudinal data has shown that greater frequency of heavy alcohol use is directly associated with poor ART adherence and an important clinical outcome (lower CD4 count) and is indirectly associated with higher HIV viral load (via lower adherence).¹⁰ Based on this evidence, we focus on heavy alcohol use for this intervention, and restrict our sample to those reporting recent heavy/binge alcohol use.

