Session 1, at enrollment, In-person individual session combining MI-based counseling and goal setting and setting up the structural component of the intervention. During session 1 the counselor will: (1) Set-up the participant to receive payments for work via mobile and (if necessary) helping the participant set up a free mobile money account; (2) discuss short and long term life and healthy living goals, financial planning and savings goal setting (e.g., % of income to reach target savings amount in X time), set goal to transfer X% of daily earnings to a savings account, establish a separate healthcare savings; (3) feedback about AUDIT-C score and assess barriers to HIV care engagement and adherence; (4) MI-based counseling about alcohol use and HIV care engagement and adherence to develop discrepancy between their behavior and savings/life and health goals, engage client in change talk including setting specific goals, discussing barriers, and ways to overcome barriers; (5) discuss alcohol-free leisure activities; (6) provide a diary for participant to track spending and savings and time and money spent drinking.

Session 2, 2 weeks after enrollment, MI-based individual session via phone. Counselors will call participants and will: (1) review progress on alcohol and HIV care engagement and adherence goals, additional counseling as needed to set new goals, overcome barriers or reinforce positive behaviors; (2) review spending and saving diary and progress on savings; (3) review participant's receipt of work payments via mobile money, progress on savings goals, and help troubleshoot any problems.

Sessions 3 and 4, approximately 4 and 6 weeks after enrollment, Group sessions with 4-8 participants per group. Each session will consist of a counselor-led group discussion: (1) encouraging participants to share with the group their life and savings goals, experience with savings, motivations to save, benefits to saving, and long term planning for healthy living; (2) discussing alcohol-free leisure activities and generate motivation to engage in alcohol-free leisure activities; (3) reinforce discrepancy between risky alcohol use and not being engaged in care, not adhering to ART, and long term goals; (4) group "problem solving" about overcoming challenges to reducing alcohol use, including participating in alcohol-free leisure activities, HIV care engagement, and ARV adherence including HIV stigma.

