We will conduct a stage 1b pilot randomized controlled trial of the intervention. As a pilot study, this study is not powered to detect differences in outcomes, but rather to obtain reliable estimates of effect sizes for a subsequent efficacy trial. However, for illustrative purposes we explore power assuming a small effect size ($d= 0.2$) which is consistent with most brief MI-based alcohol intervention study effect sizes^{17, 25-27} as well as care engagement interventions.²⁸⁻³² **We plan to enroll 160 participants in the pilot intervention trial** with 80 in each arm i.e., randomizing to the KISOBOKA intervention arm (n=80) or to the control arm (n=80, alcohol screening and referral). To be conservative we anticipate 25% attrition. This will provide 72% power to detect an intervention effect and 85% power to detect a study arm x time effect.

Sampling procedure for the randomized pilot intervention trial (n=160).

The participants recruited (based on the inclusion and exclusion criteria) from the Mildmay HIV clinics in Wakiso District will be requested to share the research assistant's contact details (phone numbers) with their potentially eligible friends. This snowball-sampling procedure will enable us to reach more participants in this hard-to-reach population. Those interested in participating in the study will contact the research assistant who will then take them through subsequent eligibility screening and recruitment procedures. This process will be repeated until the required sample is attained.

Randomization for stage 1b randomized pilot intervention trial.

Individual-level randomization with permuted block assignment balancing 1:1 will be used to create equal size groups for the two study arms. Blocks of 8 or 10 study-generated ID numbers will be created and randomly assigned to intervention or control. Once a participant is screened as eligible and attends an enrollment/baseline visit they will be assigned a study-generated ID number from the pre-randomized list which determined their study arm assignment.

Study variables

Dependent variables

Primary outcomes:

- Phosphatidylethanol (PEth) (alcohol biomarker, blood sample)
- AUDIT-C score¹⁹
- ART adherence³³

Secondary outcomes:

- HIV care engagement
- HIV viral load obtained from clinic records
- Frequency of heavy/binge drinking

Potential covariates

- Receipt of instrumental and emotional social support³⁴

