Data security: Data directly entered from the questionnaire interviews will be automatically encrypted and then uploaded onto a secure server. Only the PIs and data manager will have access to the server. No participant names will be stored in the database. All participants will be identified by a unique identifier, a random number assigned to them at the time of recruitment. In the event of loss of data or theft, all data files will be encrypted, and no outside user would be able to access the data. To ensure that no data that is collected is lost, encrypted data will be backed up on several sources: a separate server and copied to a secondary encrypted database used by the PI and biostatistician for additional processing.

Statistical Analysis Plan

A key objective of this study is to explore the effectiveness of the intervention vs. control and obtain effect size estimates to be used to design a future trial of this intervention. The primary outcomes are PEth scores, AUDIT-C score, and ARV adherence. Different statistical methods will be utilized depending on the type of outcome variable and whether minimum conditions for use of the methods are met. For example, log Gamma models may be used to analyze the difference in PEth scores between intervention and control groups given the expected distribution of PEth scores. An intent to treat approach will be utilized to determine analytic sample. Variables (except PEth which is measured at 2) will be measured at three time points (baseline, 3 and 6 months) so the dependency from the repeated measures must be considered. Information criterion such as AIC and BIC will be used to select the most appropriate covariance structure to address dependence. Generalized estimating equations (GEE) will be built to examine the intervention effect on our outcomes of interest across time points (baseline, 3 and 6 months), adjusting for repeated measurement, using a time*condition interaction term. Potential covariates for each adjusted model will be identified a priori from the literature and added to the model. Correlation matrices will be determined based on model fit. Statistically significant covariates will be retained in final fitted models using an alpha of 0.05.

4 Ethical considerations

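### Only intervention men meet in groups of 4-8, but the analysis allows only for repeated measures; if outcomes correlate within groups, the intervals are modestly too narrow

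*Combined protocol and SAP*

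**What the plan says.** Section 3.2 (Randomization) allocates individual men: "Individual-level randomization with permuted block assignment balancing 1:1 will be used". Under Intervention content and structure, the intervention has four sessions over six weeks. Two are individual. Sessions 3 and 4, at about weeks 4 and 6, are counsellor-led "Group sessions with 4-8 participants per group". The control arm receives one feedback-and-referral session of about 20 minutes, and no group is described for it.

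The Statistical Analysis Plan in section 3.5 names one source of dependence. Most variables are measured three times, "so the dependency from the repeated measures must be considered". The GEE is described as "adjusting for repeated measurement, using a time*condition interaction term", and the choice of covariance structure serves that same purpose. For PEth, "log Gamma models may be used to analyze the difference in PEth scores". Neither the analysis plan nor the sample size section mentions a treatment-group identifier, a group-level variance or an ICC.

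Two further facts bear on the remedy. Section 3.1 says "The study will take place at 5 HIV clinics in Wakiso District", but clinic is not named as a stratification factor or covariate. Covariates are also subject to a selection rule: "Statistically significant covariates will be retained in final fitted models using an alpha of 0.05".

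**The concern.** The design is partially nested: outcomes can be clustered by treatment group in one arm and not in the other. The group sessions are meant to make men influence one another, through shared goals, motivation and joint problem solving, so some correlation within groups is possible. A robust variance clustered on the man does not capture it.

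The stake is precision. The sample size section gives the purpose as to "obtain reliable estimates of effect sizes for a subsequent efficacy trial", and an interval that is too narrow overstates that reliability. A later trial of the same group-based intervention would also want a group ICC, and this plan would not report one. If group membership is not recorded, neither the corrected interval nor the ICC can readily be recovered afterwards.

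**Working it through.** **Plan's own figures.** The plan gives no ICC or design effect to reproduce. The sample size section states 72% and 85% power. A simple two-sided comparison with d = 0.2 and 60 men per arm gives about 19%, so those figures need inputs that are not stated. That is a separate matter, and nothing below uses them.

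**Inputs.** From section 3.2: 80 men per arm, groups of 4-8, and 25% attrition. This leaves 0.75 × 80 = 60 men per arm and m = 0.75 × 4 to 0.75 × 8 = 3 to 6 analysed men per group. Assumed: ICC 0.01-0.10, and a two-sided 5% level (the SAP states 0.05 only for retaining covariates).

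**Formula, one visit, equal arms.** The design effect DE = 1 + (m − 1) × ICC applies to the intervention arm only. True SE / reported SE = √((DE + 1)/2). Type I error = 2 × (1 − Φ(1.96 / ratio)).

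Example at m = 6, ICC 0.05: DE = 1 + 5 × 0.05 = 1.25; ratio = √(2.25/2) = 1.061; type I error = 6.5%.

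| ICC | SE ratio, m = 3 to 6 | Type I error | Coverage |
|---|---|---|---|
| 0.01 | 1.005-1.012 | 5.1-5.3% | 94.9-94.7% |
| 0.02 | 1.010-1.025 | 5.2-5.6% | 94.8-94.4% |
| 0.05 | 1.025-1.061 | 5.6-6.5% | 94.4-93.5% |
| 0.10 | 1.049-1.118 | 6.2-8.0% | 93.8-92.0% |

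If no man were lost and every group had 8, the ratios would be 1.084 at ICC 0.05 and 1.162 at 0.10.

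**In effect-size units.** With 60 per arm, the 95% half-width for d at one visit is about 1.96 × √(2/60) = 0.36. At ICC 0.05 it becomes 0.36 × 1.025 to 0.36 × 1.061, about 0.37-0.38.

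**Outcome SD.** The expected sample variance in the intervention arm is 1 − (m − 1) × ICC/(n − 1). At m = 6, ICC 0.10 and n = 60 this is 1 − 0.5/59 = 0.992, or 0.8% low.

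**Three visits.** A simulation of the time-by-arm contrast at 6 months assumed groups formed within clinic, 25% random loss and within-man correlation 0.3-0.7. The true SE was 3.0-7.2% larger at ICC 0.05 and 4.6-14.7% larger at 0.10. The group effect was held at full size to month 6.

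**Cost of imposing an independence working correlation.** Take two visits, unit variance and no group effect. Per arm, the variance of the baseline-to-6-month change is:
- independence: 1/60 + 1/80 − 2r/80;
- exchangeable: (1 − r²)/60 + (1 − r)²/80.

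At r = 0.5 these are 0.01667 and 0.01563, so the SE under independence is √(0.01667/0.01563) = 1.033 times as large. At r = 0.3 the factor is 1.009 and at r = 0.7 it is 1.10. Including three-visit cases, the loss is 0.9-1.4%, 3.3-4.5% and 10-12% at r = 0.3, 0.5 and 0.7.

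**The case against.** The strongest case against is that the size rests entirely on an assumed ICC, and that a low one is likely: half the sessions are individual and group contact ends near week 6, well before the 6-month visit. The trial is a pilot, not powered for differences, with feasibility among its central aims. Moving a half-width from 0.36 to 0.37-0.38 would hardly change the design of a later trial. All of this stands, and it keeps the point minor. It does not remove it, because reliable effect-size estimates are the stated purpose and group membership is cheap to record.

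A reader might infer that the effect estimates are biased, or that the intervals are certainly wrong. Neither follows: the point estimate is unaffected, and at ICC 0 there is no understatement.

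A reader might also infer that a group-clustered model should replace the planned analysis. The documents do not support that, for three reasons.
- They do not say that the same men meet in sessions 3 and 4. Clustering on one session may miss dependence arising in the other.
- Section 3.2 (Sampling procedure) recruits through friends, who may enrol close together and share a group. Similarity that existed before treatment, and that the baseline contrast does not remove, would be counted as group variance and make the intervals too wide.
- Making that analysis primary with an independence working correlation could lose as much real precision, at r = 0.5-0.7, as the understatement at ICC 0.05.

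**Conclusion.** The point holds in conditional form and is minor. The plan allows for correlation within a man but not within a treatment group, and only the intervention arm has groups. If outcomes are positively correlated within groups, the reported intervals are modestly too narrow. At one visit with 3-6 analysed men per group, the shortfall is small at ICC 0.01-0.02. It becomes noticeable at 0.05, and at 0.10 coverage falls to 93.8-92.0%. These figures assume the ICC, random attrition of 25%, equal arms and one stable group per man. Confidence is medium, because the documents fix neither the ICC nor the stability of the groups.

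**What to change.** **Record.** For each intervention man, record the group scheduled for session 3 and, separately, for session 4. Record counsellor and clinic for all men. Intervention sessions are already audio-recorded (section 3.3) and attendance is already counted (section 3.4).

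**Analyse.** Keep the planned analysis and its within-man working correlation; do not impose independence. Add to the SAP a pre-specified group-clustered analysis, reported beside the man-clustered one:
- Sum the sandwich contributions over the treatment group for intervention men, using the session 3 group as scheduled, whatever the attendance. Sum over the man for controls and for men never scheduled to a group.
- Use a small-sample correction with t-based degrees of freedom (for example CR2 with Satterthwaite), since there are only about 80/8 = 10 to 80/4 = 20 groups. In simulations of a three-visit group-clustered analysis with clinic-by-visit terms, type I error was 6.6-8.9% uncorrected and 4.7-5.4% corrected. The uncorrected version can therefore perform worse than the plan.
- Include clinic as a fixed effect where the data allow, exempt from the significance-based retention rule. Otherwise, if groups form within clinics (the documents do not say), clinic differences shared by both arms are counted as group variance.
- If membership differs between sessions 3 and 4, repeat with the session 4 groups and state that clustering on one session misses dependence from the other.
- Report the group ICC with its interval, as descriptive only.

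**Cost.** Three recorded identifiers, one extra analysis, and slightly wider intervals in that analysis. They may be somewhat too wide if friends share a group. Counsellor-level dependence is not addressed. The exact combination proposed here, with the planned working correlation kept, was not simulated, so its calibration should be checked under the final model, particularly if log Gamma is used for PEth.

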3.4 Measures

Unless otherwise noted all variables will be assessed at baseline and at follow-up, 3 and 6 months from baseline.

Primary alcohol outcome. We will use an **alcohol biomarker**: phosphatidylethanol (PEth) as the primary alcohol outcomes assessed at baseline and 6-month follow-up. PEth is a phospholipid which is formed only in the presence of alcohol and thus is highly specific.⁴⁷ PEth has shown good performance as a medium-term biomarker⁴⁸ and in controlled laboratory studies, correlated well with level of consumption (Spearman's $r = 0.6-0.8$).⁴⁹⁻⁵²

We will also use the AUDIT-C¹⁹ as another measure of hazardous alcohol use.

ART adherence: We will assess adherence to ART using the AIDS Clinical Trials Group Adherence measures (AACTG),⁵³ which includes recall questions about ARVs missed for the previous 4 days prior to the interview. It has demonstrated construct validity in Uganda and similar settings⁵⁴ and shows strong correlations with HIV VL⁵⁵ and moderate correlations with electronic adherence monitoring.⁵⁶

Measures and analysis for assessment of feasibility:

To inform a future larger randomized trial of the *KISOBOKA* intervention we follow Bowen et al.'s suggestions for conducting feasibility studies in preparation for larger RCTs²⁴ which includes assessing feasibility on the following dimensions: **acceptability, demand/use, implementation, and practicality**. We will document the number of intervention sessions participants attended which will speak to demand for/use of the intervention. To monitor implementation for the individual and group intervention sessions we will audio record intervention sessions and transcribe and code 20% of sessions to monitor intervention fidelity. Related to the practicality of the procedures, we will assess our retention rate through the 6-month follow-up to determine if we will need to develop additional retention procedures to maximize retention in a larger trial with a longer follow-up.

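### The stated 72% and 85% power at d = 0.2 cannot be verified from the inputs given, and both exceed what about 60 per arm provides for a 0.2 SD effect at moderate within-person correlation

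*Combined protocol and SAP*

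**What the plan says.** Section 3.2, under the sample-size heading for the randomized pilot, says that "this study is not powered to detect differences in outcomes, but rather to obtain reliable estimates of effect sizes for a subsequent efficacy trial". It continues that "for illustrative purposes we explore power assuming a small effect size", given as d = 0.2. Enrolment is 160, 80 per arm, and "To be conservative we anticipate 25% attrition". The conclusion is then stated without qualification: "This will provide 72% power to detect an intervention effect and 85% power to detect a study arm x time effect".

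The rest of the plan does not supply the missing inputs:

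- Section 3.4 has "phosphatidylethanol (PEth) as the primary alcohol outcomes assessed at baseline and 6-month follow-up", so PEth has one follow-up value. Section 3.5 says the other variables are measured three times (baseline, 3 and 6 months).
- The Statistical Analysis Plan in section 3.5 says that "log Gamma models may be used to analyze the difference in PEth scores between intervention and control groups". For the outcomes across visits it plans GEE, "adjusting for repeated measurement, using a time*condition interaction term", with the correlation structure left to model fit.
- The only alpha in the plan, 0.05, is for retaining covariates.

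**The concern.** An unadjusted two-group comparison with 60 per arm has about 19% power for a 0.2 SD difference. Repeated measures and baseline adjustment raise this, but by how much depends on the within-person correlation, which is not given. It is also unclear which test the 72% belongs to, because the analysis plan examines the intervention effect through the time-by-condition term, and that is the term to which the 85% is attached.

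These are the only figures that say what 160 participants can show, and the pilot is meant to supply effect sizes for an efficacy trial. A reader who relies on 72–85% could take a non-significant pilot result as evidence against a 0.2 SD effect, when the chance of detecting such an effect may be well under a half.

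**Working it through.** **Inputs from the plan.** d = 0.2; 80 per arm; 25% attrition, so n = 80 × 0.75 = 60 per arm; three visits, or two for PEth.

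**Assumed, because the plan does not give them.** Two-sided alpha 0.05; d is a difference of 0.2 SD; equal correlation ρ between any two visits, 0.5 to 0.7; normal-scale outcome. This approximates the GEE; a log-gamma model for PEth may differ.

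**Formula.** For a contrast with variance factor v (in units of the outcome variance), the noncentrality is 0.2 / √(2v/60), and power comes from the noncentral t with 118 df. For a single unadjusted visit v = 1: 0.2 / √(2/60) = 0.2 / 0.183 = 1.095, which gives 19.2%.

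| Contrast | v | ρ = 0.5 | ρ = 0.6 | ρ = 0.7 |
|---|---|---|---|---|
| 6 months, baseline-adjusted (fits PEth) | 1 − ρ² | 24.1% | 27.4% | 33.1% |
| Mean of months 3 and 6, baseline-adjusted | (1 + ρ)/2 − ρ² | 33.6% | 37.4% | 44.1% |
| Arm by time: change to 6 months | 2(1 − ρ) | 19.2% | 22.9% | 28.9% |
| Arm by time: follow-up mean minus baseline | 1.5(1 − ρ) | 24.1% | 28.9% | 36.7% |
| Arm by time: 2-df F test, pattern (0, 0.2, 0.2) | – | 18.6% | 22.3% | 28.6% |

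**Can the plan's figures be reproduced?**

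1. *By relaxing other inputs, ρ 0.5–0.7.* With no attrition (80 per arm), the two baseline-adjusted contrasts give 31–42% and 43–55%, and arm by time gives 24–47%. With alpha 0.10 at 60 per arm, they give 35–45%, 46–57% and 29–49%. None reaches 72% or 85%.

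2. *By a high correlation.* At 0.2 SD, 72% needs ρ = 0.866 (two-visit mean) or 0.904 (one follow-up). For arm by time, 85% needs ρ = 0.912 (mean minus baseline), 0.928 (2 df) or 0.934 (6-month change). One common ρ of 0.908 gives 73.7% for the baseline-adjusted 6-month comparison and 83.3% for follow-up mean minus baseline, but the two tests then use different visits.

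3. *With the same visits for both tests.* The change contrast has the larger variance: 2(1 − ρ) − (1 − ρ²) = (1 − ρ)², and 1.5(1 − ρ) − [(1 + ρ)/2 − ρ²] = (1 − ρ)². At equal d, ρ and alpha, arm by time therefore cannot have more power than the baseline-adjusted effect, yet the plan states 85% against 72%. An unadjusted arm effect averaged over three visits reaches at most 47%, at ρ = 0.

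4. *By reading the effect as Cohen's f.* A repeated-measures interaction formula with f = 0.1, N = 120, three visits and ρ = 0.67 gives 84.5%. That f corresponds to a difference in change of 0.42 SD for pattern (0, D, D) or 0.49 SD for (0, D/2, D), and the same settings give 23% for the arm effect. A between-arm f = 0.2 with three visits and ρ = 0.6 gives 72%, but that f is d = 0.4.

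**Effect needed at 60 per arm, ρ from 0.5 to 0.7.** For 72%: 0.41 to 0.33 SD (one follow-up) or 0.33 to 0.28 SD (two-visit mean), baseline-adjusted. For 85% arm by time: between 0.55 and 0.37 SD, depending on contrast and ρ.

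**Precision.** The unadjusted standard error is √(2/60) = 0.183 SD, so the 95% half-width is 1.96 × 0.183 = 0.36 SD. The effect detectable with 80% power is 0.52 SD.

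**The case against.** The strongest reply is that the plan contains no contradiction. It gives no correlation, alpha or test, so the shortfall rests on values brought in from outside, and the result is sensitive to them: at ρ = 0.9 the baseline-adjusted powers are 70% (6 months) and 83% (two-visit mean), and follow-up mean minus baseline has 80%. The f = 0.1 interaction formula at ρ = 0.65 gives 73.8% with two visits and 82.2% with three, so an undefined scale for d may be the real source. The same paragraph also calls the calculation illustrative and says the pilot is not powered, and no stopping or progression rule uses the figures.

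Much of this stands. The shortfall is conditional on ρ, and the practical harm is small. But a high ρ comes close to both figures only when the two tests use different visits, and the f-based route needs a difference in change of about 0.4 SD or more and makes both figures interaction tests, whereas the plan lists an intervention effect separately. The illustrative label limits the weight of the statement. It does not make the percentages right for the effect named beside them.

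**Conclusion.** The concern holds. As written, the two powers cannot be verified. For a 0.2 SD effect with 60 per arm, two-sided 0.05 and ρ of 0.5 to 0.7, the stated 72% compares with 24–33% (one follow-up) or 34–44% (two-visit mean), both baseline-adjusted, and the stated 85% compares with 19–37%. This rests on the assumed alpha, correlation range and SD scale, and on a normal-scale approximation. Outside that range the figures are attainable, but only under settings the plan does not state. It should be fixed as a misleading planning statement; it does not undermine the design or the analysis.

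**What to change.** Delete the 72% and 85%, or restate each with its test, alpha, sidedness, within-person correlation and number of visits, and with the contrast and scale to which d = 0.2 refers. Do this separately for PEth, which has one follow-up, and for the three-visit outcomes. Optionally add the precision figures above (half-width about 0.36 SD; about 0.52 SD detectable with 80% power), which suit a pilot whose aim is estimation.

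The cost is one reworded paragraph, and the restated powers would probably look less favourable. Enrolment, visits and analysis stay as they are.

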Exclusion criteria: visibly intoxicated at the time of enrollment (eligible to enroll when sober); does not speak Luganda or English; unable to read basic Luganda or English; currently receiving work payments via mobile money or currently uses mobile money savings services; occupation is a boat owner or engine owner.

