3.2 Study design and procedures

Intervention

Recruitment, eligibility screening, and informed consent.

We will recruit men who are patients at Mildmay's HIV clinics in Wakiso District using two methods.

- 1) After a male patient checks in for his appointment and his HIV clinic record is pulled, a clinic staff member will review the patient's records to determine if they may be potentially eligible (male, aged 18-50, on ART for at least 6 months, work in the fishing industry, can be reached by phone). After the patient has completed his clinic appointment, clinic staff will refer male patients who are potentially eligible to a research assistant for eligibility screening.
- 2) Clinic staff will also review clinic records to identify potentially eligible patients and will call the patient to tell him about the study. If the patient is interested, they will seek permission to share his phone number and name with the researchers, provide the contact number for the research assistant, and offer that the patient can come to the clinic to meet the research

assistant to learn more about the study. Study staff will briefly describe the study and seek informed consent to conduct eligibility screening.

Those determined eligible will be offered participation in the study and study staff will obtain written informed consent.

Intervention content and structure

After participants complete the baseline structured interview, the research assistant will refer them to the appropriate counselor who will provide intervention participants with the *KISOBOKA* ("It is possible!"). Our proposed brief intervention consists of 4 sessions: 2 individual, 2 group over 6 weeks, plus 2 times weekly text message reminders of life/savings (family prosperity, opportunities for children) and healthy living goals. Through these sessions the combination intervention will address environmental, interpersonal, and individual level factors which are key drivers of alcohol use and key barriers to HIV care engagement and adherence in this population.

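### The study ID is itself the allocation, and nothing conceals it or holds it back until baseline data are complete, so baseline self-report could be taken with the arm known

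*Combined protocol and SAP*

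**What the plan says.** - **Method (Section 3.2, randomization paragraph).** Men are allocated individually, 1:1, in permuted blocks. On how the blocks are made, the plan says: "Blocks of 8 or 10 study-generated ID numbers will be created and randomly assigned to intervention or control".
- **Trigger (same paragraph).** "Once a participant is screened as eligible and attends an enrollment/baseline visit", the plan says, "they will be assigned a study-generated ID number from the pre-randomized list which determined their study arm assignment". The trigger is attending the visit; completing baseline is not mentioned.
- **Identifier (Section 3.5, Data security).** "All participants will be identified by a unique identifier, a random number assigned to them at the time of recruitment".
- **First use of the arm (Section 3.2, Intervention content and structure).** "After participants complete the baseline structured interview, the research assistant will refer them to the appropriate counselor".
- **Enrolment judgement (Section 3.1, exclusion criteria).** One exclusion is being "visibly intoxicated at the time of enrollment"; such a man may enrol once sober.
- **Baseline data (Sections 3.3 and 3.5).** After consent, an interviewer conducts a one-on-one interview of about 60 minutes, entered in real time, and a venous sample is taken for PEth.
- **Blinding and staffing (Section 3.3).** Blinding is stated for follow-up interviewers only. One group of research assistants/interviewers is hired for both baseline and follow-up.

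The documents do not say who holds the list, whether the link from ID to arm is hidden, or at what moment the arm is revealed.

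**The concern.** When the ID carries the arm, issuing the ID is the act of allocation. If that happens on arrival at the baseline visit, two kinds of bias become possible.

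**Reporting.** AUDIT-C and missed ART doses are answers given to an interviewer. If either party knows the arm, the baseline answers or their recording can differ between arms. The Statistical Analysis Plan treats baseline as one of the outcome time points and reads the effect from a time-by-condition interaction, so a difference at baseline goes straight into the estimate.

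**Selection.** If the next assignment can be foreseen, staff have some room to influence who enters at which place on the list. Visible intoxication is a judgement and leads to deferral. The arms also differ in what they offer participants: Section 3.2 gives about 563 paid minutes in the intervention arm and 195 in control, at 18,000 shillings per hour, a difference of (563 − 195)/60 × 18,000 = 110,400 shillings.

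There is also a later consequence. The same ID could reveal the arm to anyone who has seen the list, which would weaken the blinding stated for follow-up. The trial's stated purpose is to supply reliable effect sizes for a subsequent efficacy trial, so a bias here would be carried into that design.

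**Working it through.** The plan states no figure on this point, so there is nothing to reproduce. The check compares the sections and adds two illustrations.

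**1. Order of events.**

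| Event | Source | Timing given |
|---|---|---|
| Eligibility screening | 3.2, randomization | Before the ID |
| ID, and therefore arm, assigned | 3.2, randomization | On attending the enrolment/baseline visit |
| Identifier assigned | 3.5, Data security | At recruitment; not said to be the same number |
| Baseline interview and blood | 3.3 | After consent; order relative to the ID not stated |
| Referral to the arm's counselor | 3.2, Intervention content | After the baseline interview |

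The text permits the ID to be issued before the interview and does not prohibit it. If the Section 3.5 identifier is the same number, it too precedes baseline.

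**2. Roles.** Research assistants screen for eligibility (Section 3.2, recruitment) and refer men to the appropriate counselor after the interview. That role must therefore know the arm by the time of referral. Who hands out the ID is not stated.

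**3. Foreseeing the next assignment.** If the list is readable, every assignment is known. If it is not, but staff know past assignments and the block size, then for a 1:1 block of 2h:

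- Expected number certain in advance = 2h/(h + 1). Block of 8: 8/5 = 1.60 (20.0%). Block of 10: 10/6 = 1.67 (16.7%).
- Expected number guessed correctly = h + 2^(2h−1)/C(2h, h) − 1/2. Block of 8: 4 + 128/70 − 0.5 = 5.33 (66.6%). Block of 10: 5 + 512/252 − 0.5 = 6.53 (65.3%).

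So hiding the list still leaves some predictability if the block sizes are known.

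**4. Effect of a baseline reporting shift.** Write the contrast as (intervention follow-up − intervention baseline) − (control follow-up − control baseline). If only the intervention arm's baseline is recorded b SD too high, the contrast moves by −b. The direction in practice is unknown. Assumed range for b: 0.1 to 0.2 SD.

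- b = 0.1: bias 0.1 SD; 0.1/0.2 = 50% of the illustrative d = 0.2.
- b = 0.2: bias 0.2 SD; 0.2/0.2 = 100%.

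**5. False-positive rate with no true effect.** Inputs: 80 × (1 − 0.25) = 60 per arm, from the plan's enrolment and attrition; two-sided alpha 0.05; assumed baseline-to-follow-up correlation ρ. In SD units, SE = √[2(1 − ρ)] × √(2/60), and the rejection rate is 1 − Φ(1.96 − b/SE) + Φ(−1.96 − b/SE).

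Worked case, ρ = 0.5 and b = 0.1: SE = 1 × 0.183, b/SE = 0.548, rejection rate 8.5%.

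| ρ | b = 0.1 SD | b = 0.2 SD |
|---|---|---|
| 0.3 | 7.5% | 15.2% |
| 0.5 | 8.5% | 19.5% |
| 0.7 | 10.9% | 29.3% |

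**The case against.** The strongest reply is that this is an unreported safeguard in a short pilot protocol. The randomization paragraph gives no order within the visit, and the only uses of the arm that are described, counselor referral and control feedback, come after baseline. The Section 3.5 sentence concerns de-identification and does not mention the randomised list. Eligibility, including the drinking and missed-dose criteria, is settled before a man receives his own ID.

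Much of this stands, and it rules out several stronger readings that a reader might infer:

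- *That the plan allocates first and interviews second with the arm known.* It permits this; it does not state it.
- *That every assignment is known in advance.* This needs a readable list, and no section says staff can read it. Nor is 50% the fair comparison, since blocking alone allows about 65% to 67% if block size and history are known.
- *That the research assistant issues the ID.* The sentence is passive and names no one.
- *That reporting bias reaches all three primary outcomes.* PEth is a laboratory measure and is not affected by how an interview is conducted.
- *That follow-up blinding is already broken.* The plan asserts that blinding; the ID undermines it only for someone who has seen the list.

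What the reply does not remove is the rule itself. The arm is fixed by an ID triggered by attendance, and no section conceals the link or delays it until baseline is complete. Screening before the ID protects against use of a man's own ID, but not against foresight of the next one.

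**Conclusion.** The concern holds as a design weakness that should be corrected. As written, the procedure lets the baseline interview take place with the arm known, and lets enrolment or deferral be influenced if the list is readable or the blocks are predictable. It is not evidence that either happens.

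The reporting risk is limited to AUDIT-C and self-reported ART adherence; PEth is exposed only to selective enrolment. An assumed shift of 0.1 to 0.2 SD in one arm's baseline would bias the change contrast by 0.1 to 0.2 SD, half to all of the illustrative effect. Under the assumed correlations, the 5% error rate would rise to between 7.5% and 29.3%.

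These sizes rest on four assumptions: the shift itself, for which the documents give no figure; a shift at baseline only, since one that persisted equally at follow-up would cancel; time treated as categorical with baseline means left free; and a normal approximation with 60 per arm.

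**What to change.** 1. Give each man an arm-neutral study ID at consent and use it on all records.
2. Keep the allocation list separately, with someone who takes no part in recruitment or interviewing, and do not disclose the block sizes to recruiting staff.
3. Release the arm by sequentially numbered, opaque, sealed envelope or by central release, only after the baseline interview is submitted and the blood is drawn.
4. Have existing staff open it at the point of referral. The counselor cannot do so, because counselors are trained for one condition or the other and the arm decides which counselor is chosen.
5. Do not let anyone who learns a man's arm in this way conduct his follow-up interviews.
6. Reconcile the randomization paragraph in Section 3.2 and the Data security paragraph in Section 3.5 to this order.

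The cost is protocol wording, envelopes or a central contact, and some care in rostering interviewers, with no extra visits. If such concealment is already practised, the sponsor need only write it down and align the two sections.
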